### Discontinuation of Therapy

Patients will continue to be followed by the Department of Surgery upon discontinuation of therapy with Omegaven® for a minimum of 2 months after the treatment is stopped.

[name], Department of Surgery, Children's Hospital & Medical Center  
[name], Department of Surgery, Children's Hospital & Medical Center  
[name], Pediatric Research Office, Dept. of Pediatrics, UNMC  
[name], Department of Biostatistics, College of Public Health, UNMC

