### **D. Definition of Primary and Secondary Outcomes/Endpoints**

Generally, primary safety analyses will be based on time from baseline or 30 days after baseline until two months after patients first reached direct bilirubin levels  $< 2$  mg/dL. Baseline will be defined as information collected at the date that treatment starts for Omegaven® patients and on the date that patient reached bilirubin levels  $> 2$  for soybean oil fat emulsion patients. Information on mortality and transplant will be collected during the whole treatment with Omegaven®. Primary efficacy analysis will include time from baseline until the patient normalizes bilirubin (presents three consecutive direct bilirubin  $\leq 2$  mg/dL or a direct bilirubin  $\leq 2$  mg/dL and weaned from TPN).

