**Patients will be withdrawn from the study for any of the following:**

- a) Toxicity considered unacceptable by the Principal Investigator (i.e. Evidence of burr cell anemia (reported toxicity); Continued lipid intolerance (triglyceride >200) despite dose reduction attempts and administration modification; evidence of coagulopathy (INR > 2.0)).
- b) Patient/guardian requests to discontinue treatment and/or observation for any reason.
- c) A suitable organ has been located and the patient is able to undergo a liver or liver/intestinal transplant.
- d) Decision by the Principal Investigator that termination is in the patient's best medical interest.
- e) Patient is lost to follow up.

In the event that a patient is withdrawn from the protocol, study staff will document the date of withdrawal, the reason for withdrawal, and the results of all measurements of interest made up to date of withdrawal.

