## **DATA ANALYSIS PLAN**

Using graphical methods (including boxplots) and descriptive statistics, we will assess assumptions required for validity of statistical methods and presence of outliers. Continuous variables will be summarized via means (and standard deviations) or medians (and interquartile ranges, when appropriate. When appropriate, variables will be transformed.

Primary analyses of the primary outcome will be based on the intention-to-treat analysis i.e., patient will be considered receiving Omegaven® throughout the whole follow-up period, regardless of temporary discontinuation of treatment due to infections or other causes.

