#### *Analysis of Efficacy of Omegaven®*

The primary outcome to gain preliminary evidence of efficacy will be based on the time from baseline to normalization of bilirubin level, i.e., first time point among three consecutive in which bilirubin is < 2 mg/dL. We do not anticipate that any subject will present a rebound on direct bilirubin after normalization. However, we will describe the cohort with respect to the frequency of rebounds in bilirubin levels.

Time to normalize direct bilirubin levels will be estimated using Kaplan-Meier curves. We will estimate hazard ratios and adjust for potential baseline confounders using Cox-proportional hazard models. For all survival analysis based on non-parametric or semi-parametric methods, we will attribute an infinite time to event for subjects who die or receive a liver transplant before bilirubin is normalized. Subjects who die before their bilirubin levels normalize (particularly due to liver failure) have in fact the worst outcome (infinite time to normalize bilirubin) and were not censored before reaching the endpoint of interest. Results of these analyses will be compared with results of analysis excluding subjects who die or are transplanted. Time to reach a total bilirubin of 1.2 will also be estimated using survival analysis methods. Analyses of this outcome will proceed as described for direct bilirubin.

We will also describe individual profiles over time (i.e., 2 months before baseline or birth until end of follow-up period) for all subjects using graphical methods. Trends in liver function markers over time will be explored using generalized linear models in which correlations of observations within subjects will be accounted using a generalized equations or random effects approach. We will perform these analyses including only subjects who did not die or undergo transplantation and including all subjects but assigning for subjects who died or underwent a transplant their worse possible outcome after they died or had the transplant. Using descriptive statistics, we will also explore the association between spikes in blood tests over time and predictors including transfusions of red blood cell products and blood stream infections.

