#### **Reversal Study Lab Schedule:**

Patient Status	Parameter	Tests to be Performed	Frequency
Inpatient/receiving Omegaven®	Direct bilirubin $\geq$ 2 mg/dL	PN profile, AST, GGT, CRP, lipid Panel, PT, PTT, INR, fibrinogen, EFA Panel	Weekly
	Direct bilirubin $<$ 2 mg/dL	PN profile PN profile, AST, GGT, CRP, PT, PTT, INR, fibrinogen, EFA panel, lipid panel	Weekly Monthly

[name], Department of Surgery, Children's Hospital & Medical Center  
 [name], Department of Surgery, Children's Hospital & Medical Center  
 [name], Pediatric Research Office, Dept. of Pediatrics, UNMC  
 [name], Department of Biostatistics, College of Public Health, UNMC

Inpatient/off Omegaven®	Direct bilirubin $\geq$ 2 mg/dL	PN profile	Weekly
	Direct bilirubin < 2 mg/dL	PN profile, AST, GGT, CRP, lipid Panel, PT, PTT, INR, fibrinogen, EFA Panel	one complete set of post-Omegaven labs
Outpatient/on Omegaven®	Direct bilirubin $\geq$ 2 mg/dL	PN profile, AST, GGT, CRP, lipid Panel, PT, PTT, INR, fibrinogen, EFA Panel	Weekly
	Direct bilirubin < 2mg/dL	PN profile, AST, GGT, CRP, lipid Panel, PT, PTT, INR, fibrinogen, EFA Panel	Monthly until off Omegaven and at least 1 direct serum bilirubin < 2 mg/dL

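### Death and transplant have no stated collection route after study withdrawal, although the primary efficacy rule depends on them, so the normalisation rate may be overstated if withdrawal follows poor prognosis

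*Protocol*

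**What the plan says.** On collection, section D (Definition of Primary and Secondary Outcomes/Endpoints) states: "Information on mortality and transplant will be collected during the whole treatment with Omegaven". No later window for these two events is given anywhere.

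The list at the end of section G concerns withdrawal from the study, not only from the drug. Its reasons include "Toxicity considered unacceptable by the Principal Investigator" (one example is INR above 2.0), a decision by the investigator, and "A suitable organ has been located and the patient is able to undergo a liver or liver/intestinal transplant". At withdrawal, staff record the date, the reason and "the results of all measurements of interest made up to date of withdrawal". Section G also ends adverse-event reporting at study exit.

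On analysis, the Data Analysis Plan says "Primary analyses of the primary outcome will be based on the intention-to-treat analysis". It explains this as counting the child as treated throughout despite temporary interruptions, and does not mention permanent discontinuation. Analysis of Efficacy of Omegaven® uses Kaplan-Meier and Cox methods and adds: "we will attribute an infinite time to event for subjects who die or receive a liver transplant before bilirubin is normalized". It gives no rule for a child withdrawn alive.

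Two places do look past the end of treatment. Discontinuation of Therapy has the surgical department follow patients "for a minimum of 2 months after the treatment is stopped". The Reversal Study Lab Schedule gives inpatients off Omegaven® a weekly profile while direct bilirubin is at least 2 mg/dL and "one complete set of post-Omegaven labs" when it is below 2. It has no row for outpatients off Omegaven®. Neither place names death or transplant or says that its data enter the analysis.

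**The concern.** The infinite-time rule exists so that children with the worst outcome are not treated as if they might still have normalised. It can work only if those outcomes are known. A child withdrawn with coagulopathy who dies some weeks later is a child the rule is meant for, yet the stated windows for collecting the event have closed by then.

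With data ending at withdrawal, the default in Kaplan-Meier and Cox analysis is to censor there. That assumes a withdrawn child has the same chance of normalising as a child who stays. If withdrawal is more common in children who are doing badly, the assumption fails in the direction that favours Omegaven®. Hypothesis 2.4, on transplant and hepatic death, is exposed more directly, because events after withdrawal may simply not be counted.

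A statistical analysis plan can set a censoring rule, but it cannot restore outcomes that were never collected. The collection window is fixed in the protocol.

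**Working it through.** **Step 1: trace each course through the text.**

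| Child's course | Stated route for recording | Effect on the primary analysis |
|---|---|---|
| Dies or is transplanted on treatment before normalising | Section D window | Infinite time |
| Transplant is the reason for withdrawal | Date and reason documented at withdrawal | Infinite time |
| Withdrawn for toxicity or by investigator decision, later dies or is transplanted | None stated: treatment has ended and the child has left the study | The rule applies by its wording, but the event may not be known |
| Withdrawn alive, bilirubin normalises later | Inpatient labs only, not linked to the analysis | May not be known |

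The gap lies in the last two rows.

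**Step 2: counting example.** The protocol states no normalisation or withdrawal rate, so there is no figure of its own to reproduce. All inputs here are assumed, except that 25 is one of the sample sizes in Table 4. Of 25 children, 15 normalise, 5 die or are transplanted on treatment, and 5 are withdrawn before the first normalisation.

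- Kaplan-Meier, censoring the 5 at withdrawal: 15/(25 − 5) = 15/20 = 75%.
- Full follow-up, none of the 5 normalises: 15/25 = 60%.
- Full follow-up, all 5 normalise: 20/25 = 80%.

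The true figure can lie on either side of 75%.

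**Step 3: bias at 24 weeks.** Assumptions, none from the protocol: exponential time to normalisation with median 12 weeks, so h = ln 2/12 = 0.0578 per week; a proportion w of children assigned a withdrawal time T, uniform on weeks 2 to 12; and a hazard of normalising after withdrawal equal to r times that before it. Deaths on treatment are left out.

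- Kaplan-Meier with censoring at withdrawal estimates 1 − exp(−24h) = 1 − 0.25 = 75%.
- Overstatement = w × [exp(−24rh) × E{exp((r − 1)hT)} − exp(−24h)].

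For r = 0 (no withdrawn child later normalises), E{exp(−hT)} = (0.8909 − 0.5)/(10 × 0.0578) = 0.677, and the bracket is 0.677 − 0.25 = 0.427. For r = 0.5 it is 0.5 × 0.820 − 0.25 = 0.160. For r = 1 it is 0.25 − 0.25 = 0. For r = 1.5 it is 0.125 × 1.228 − 0.25 = −0.096.

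| Hazard ratio after withdrawal | w = 5% | 10% | 20% | 30% |
|---|---|---|---|---|
| 0 | +2.1 | +4.3 | +8.5 | +12.8 |
| 0.5 | +0.8 | +1.6 | +3.2 | +4.8 |
| 1 | 0 | 0 | 0 | 0 |
| 1.5 | −0.5 | −1.0 | −1.9 | −2.9 |

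Entries are percentage points, Kaplan-Meier minus truth. A simulation of 200,000 children per setting agrees to within 0.1 point. Some children assigned to withdraw normalise first, so w of 5% to 30% means 0.677 × w, or about 3% to 20%, actually withdrawn before normalising.

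**The case against.** Several stronger readings are tempting, and the protocol does not support them.

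- **That deaths and transplants are collected only on treatment and all data stop at withdrawal.** Section D does not say only. Read beside the general safety window, which closes two months after direct bilirubin first falls below 2 mg/dL, its sentence lengthens collection. The withdrawal paragraph lists what must be documented and does not forbid later collection. The two-month follow-up, the inpatient labs and the chart review in section E give partial cover.
- **That withdrawn children are censored.** No passage says so. It is the default when data end, and the rule may lie in an analysis plan that was not available.
- **That transplants are lost.** A transplant that triggers withdrawal is documented as the reason and falls under the infinite-time rule.
- **That the intention-to-treat statement is contradicted.** Its explanation names temporary interruption only. It leaves a gap on permanent discontinuation and conflicts with nothing.
- **That the rate is overstated.** The counting example allows a truth of 60% to 80% around an estimate of 75%. Guardian request and loss to follow-up, for example, are not tied by the protocol to failure to normalise.

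It is also fair that the study is non-randomised, describes its efficacy evidence as preliminary and takes its size from compassionate use.

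These points remove the certainty and the direction. They do not supply a route by which a death or transplant after withdrawal must be recorded and analysed. The post-treatment follow-up names no outcomes, and its lab schedule omits outpatients off Omegaven®.

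**Conclusion.** The point holds as a gap between outcome collection and analysis. Followed as written, a child withdrawn for toxicity or by investigator decision who later dies or is transplanted may never come under the infinite-time rule, and the event may be missed for hypothesis 2.4.

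The effect on the normalisation rate depends on why children leave: overstated if withdrawal is related to poor prognosis, unbiased if unrelated, understated if prognosis is better. A link to poor prognosis is plausible for withdrawal with INR above 2.0, but the protocol does not establish it. Under the assumed 12-week median and withdrawal in weeks 2 to 12, the overstatement is about 2 to 13 points if 5–30% are assigned to withdraw and none later normalises, and about 1 to 5 points if their hazard halves. These are illustrations, not estimates for this trial. With the 20 to 30 children considered in Table 4, a few such cases could matter.

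**What to change.** - **Collection.** Amend section D and the withdrawal paragraph in section G so that death, transplant and direct bilirubin are collected from chart, Epic or clinic records for every treated child until normalisation, death, transplant or a common data cut-off, regardless of treatment or withdrawal and subject to consent. At minimum, cover the two months already promised under Discontinuation of Therapy. This should add to the treatment-long window now stated, not shorten it.
- **Primary analysis.** State that the infinite-time rule applies to deaths and transplants after withdrawal, and extend the intention-to-treat wording to permanent discontinuation.
- **Children withdrawn with no later data.** Show a sensitivity analysis that treats toxicity and investigator-decision withdrawals as not normalised, alongside censoring at withdrawal. Treating them as not normalised should not be the primary rule, because it replaces one untestable assumption with another and can bias the rate downward.

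The cost is protocol wording and some chart review, using sources that section E already names, with no new procedures. The reported normalisation rate may become less favourable. The change is best made before follow-up on withdrawn children is lost.

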### Outcome/Endpoints

#### *Treatment safety*

Our primary outcome for treatment safety will be based on patient's essential fatty acid profile. We will compare patients before treatment with Omegaven® started and after treatment started (one month after treatment started until treatment stopped) with respect to the frequency with which triene/tetraene ratio  $> 0.2$  at any time. Primary analyses for these and all other safety outcomes will be based on a follow-up time for Omegaven® starting 30 days after baseline, i.e., 30 days after treatment started for Omegaven® patients and 2 months after the first direct bilirubin level  $< 2$  mg/dL was recorded.

Additional comparisons across treatment periods for subjects receiving Omegaven® will be aimed to assess occurrence of spontaneous bleeding (e.g., unexplained bruising, oozing from gums/incision sites), and maximum triene/tetraene ratio, minimum platelets, maximum international normalized ratio (INR), and trends in pre-albumin (age standardized levels). We will also explore trends in coagulopathies based on curves of platelets, prothrombin time (PT), partial thromboplastin time (PTT) over time, and INR. We will also describe the rate with which INR ratios were  $> 2$  (number of days/follow-up time), as a marker of coagulopathies.

Additional evaluation of Omegaven® will be performed with regards to rate in which albumin is  $> 3$  g/dL, maximum triglyceride level, rate of blood stream infections (number of positive blood cultures/follow-up-time under PN after baseline), rate of central venous catheter (CVC) infections (number of CVC infections/follow-up time and number of gram positive CVC infections/follow-up time), and occurrence of anaphylactic reactions after baseline.

We will describe trends over time for all outcomes associated with fatty acid profiles (including triene/tetraene ratios, triglycerides, total omega-6 fatty acids, total omega-3 fatty acids, total saturated, total monounsaturated, and total polysaturated fatty acids). Specific fatty acids such as arachidonic, palmoleic, palmitic, oleic, stearic, and linoleic fatty acids will also be evaluated and described.

[name], Department of Surgery, Children's Hospital & Medical Center  
[name], Department of Surgery, Children's Hospital & Medical Center  
[name], Pediatric Research Office, Dept. of Pediatrics, UNMC  
[name], Department of Biostatistics, College of Public Health, UNMC

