### *Analysis of Safety and Tolerability of Omegaven®*

All primary safety and tolerability analyses will be based on descriptive statistics. In secondary analyses, we will also assess the statistical significance of differences. The period receiving Omegaven® will start 30 days after beginning PN with Omegaven® for the main analysis. Outcomes measured in the Omegaven® will be described for a period starting 30 days after baseline.

Primary outcomes measured will include whether the triene/tetraene ratio was ever  $> 0.2$  during the intervention period and whether the INR was ever  $> 2$ . Secondary outcomes measured will include platelets, prothrombin time (PT), partial thromboplastin time (PTT), and other components of the fatty acid profile. Analysis of all categorical outcomes will be based on proportions and of all continuous outcomes will be based on means or medians of the individual mean, maximum or minimum values, as appropriate, during the respective follow-up period. Comparisons between periods (pre and post-treatment) will be performed based on paired tests, parametric or non-parametric, as appropriate. We will also explore trends over time (e.g., decreasing for INR and increasing for pre-albumin) and estimate p-values via regression models using generalized estimating equations or random effects to account for within subject correlations. When describing outcomes over time, we will explore the effect of predictors of poor hepatic outcomes, such as use of antifungal agents (e.g., amphotericin) and antidiarrheal agents (e.g., loperamide), on potential spikes.

[name], Department of Surgery, Children's Hospital & Medical Center  
[name], Department of Surgery, Children's Hospital & Medical Center  
[name], Pediatric Research Office, Dept. of Pediatrics, UNMC  
[name], Department of Biostatistics, College of Public Health, UNMC

We will also evaluate nutritional outcomes including difference in weight-for- age Z-scores and height-for-age Z-scores from baseline to the moment in which the child starts enteral feeding and to the moment in which the child receives less than 10% of their calories from PN. Using linear regression, we will explore adjustment for baseline alternative predictors of interest. Trends over time in Z-scores will also be explored using regression with repeated measure methods.

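### The before/after contrast on triene/tetraene above 0.2 'at any time' depends on how often each child is tested; at the required minimum schedule it shows a rise with no true change

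*Protocol*

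**What the plan says.** All references are to the Protocol.

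- **Primary contrast (Treatment safety).** "We will compare patients before treatment with Omegaven® started and after treatment started", by the frequency of a triene/tetraene ratio above 0.2 at any time. No start or length is given for the period before treatment.
- **Further contrasts (same section).** "Additional comparisons across treatment periods for subjects receiving Omegaven® will be aimed to assess occurrence of spontaneous bleeding", and also maximum triene/tetraene, minimum platelets and maximum INR.
- **On-treatment window (same section).** Two versions appear. The first runs from one month after the start until treatment stops. The second is "Primary analyses for these and all other safety outcomes will be based on a follow-up time for Omegaven® starting 30 days after baseline" and ends two months after the first direct bilirubin below 2 mg/dL.
- **Analysis of Safety and Tolerability.** The 'ever above 0.2' outcome is stated for the on-treatment period: "during the intervention period and whether the INR was ever" above 2. INR ever above 2 enters a before/after comparison only through a general sentence: "Comparisons between periods (pre and post-treatment) will be performed based on paired tests, parametric or non-parametric, as appropriate". Primary safety analyses are descriptive, and significance is secondary.
- **Testing (Safety Labs Schedule; Appendix Table 2).** Fatty-acid profiles are required once at baseline and then monthly. Coagulation labs are required once at baseline, weekly while direct bilirubin stays at or above 2 mg/dL, and monthly after that. Both tables call this a minimum. The Reversal Study Lab Schedule lists the essential fatty acid panel weekly while direct bilirubin is 2 mg/dL or more.
- **Hypothesis 1.1.** Fatty-acid deficiency will be no more frequent on Omegaven than before it.

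**The concern.** Whether a ratio was ever above 0.2, and the maximum or minimum of a series, become more extreme as tests accumulate. Here they are compared between two periods with different numbers of tests. One required profile on one side and several on the other will make an unchanged child look worse on treatment.

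This contrast is the one aimed at hypothesis 1.1. Because the primary analysis is descriptive, readers will rely on the two proportions side by side. A difference produced by the testing schedule could then be read as deficiency caused by Omegaven.

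**Working it through.** **Plan's own figure.** The only figure for a before/after comparison is Table 4, McNemar power at given discordance. It does not address unequal testing, and this point does not rest on it. (Separately, its first row prints 59/72/81% where a two-sided 5% exact test gives 46/60/71%; a one-sided 5% exact test matches all 18 cells.)

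**Number of on-treatment tests, k.** Let T be the day of the first direct bilirubin below 2 mg/dL. T is assumed. The second window runs from day 30 to day T + 60.

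| Testing | T = 60 | T = 120 |
|---|---|---|
| Monthly minimum, day-30 test excluded/included | 3 / 4 | 5 / 6 |
| Weekly to T, then two monthly | 4 + 2 = 6 | 13 + 2 = 15 |

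The window that runs until treatment stops gives more tests whenever treatment outlasts day T + 60.

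**'Ever' with no true change.** The per-test rate p is the same in both periods; p is an assumption.

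- Independent tests: P(ever) = 1 − (1 − p)^k. For p = 0.05, k = 4: 1 − 0.95^4 = 0.185.
- Strong variation between patients (patient rates follow a beta distribution, a + b = 2, mean p): P(ever) = 1 − product over j = 0 to k − 1 of (b + j)/(2 + j), with b = 2(1 − p). For p = 0.05, k = 4: 1 − 0.950 × 0.967 × 0.975 × 0.980 = 0.123.

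Ranges run from strong between-patient variation to independence:

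| p per test | Before (1 test) | k = 3 | k = 4 | k = 6 |
|---|---|---|---|---|
| 1% | 1% | 2.2-3.0% | 2.5-3.9% | 3.1-5.9% |
| 2% | 2% | 4.3-5.9% | 5.0-7.8% | 6.2-11.4% |
| 5% | 5% | 10.5-14.3% | 12.3-18.5% | 14.9-26.5% |
| 10% | 10% | 20.2-27.1% | 23.4-34.4% | 28.1-46.9% |

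In 30 patients with k = 4, 1% per test means 0.3 expected before and 0.8-1.2 on treatment; 5% means 1.5 and 3.7-5.6.

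**More pre-treatment tests** (p = 5%, four on treatment, so 12-19% on treatment): two before give 8-10%; four before give the same 12-19%; eight before give 17-34%, which reverses the contrast.

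**Secondary exact McNemar test, two-sided 5%, one test before.** For independent tests the discordant probabilities are (1 − p)(1 − (1 − p)^k) and p(1 − p)^k. At p = 5%, k = 4 these are 0.95 × 0.185 = 0.176 and 0.05 × 0.815 = 0.041. False rejection, same range as above:

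| p, k | n = 20 | n = 30 |
|---|---|---|
| 5%, 4 | 0.5-6.9% | 3.0-19.8% |
| 5%, 6 | 1.5-24% | 8-50% |
| 2%, 4 | at most 0.2% | at most 1.5% |
| 1%, 6 | below 0.1% | at most 0.5% |

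**Maxima.** The expected maximum of three normal values is 0.85 within-patient SD above that of one value and 0.85 − 0.56 = 0.29 SD above that of two. Simulated paired t test, n = 25, three on-treatment tests, independent normal values: false rejection is about 90% with one pre-treatment test, 23% with two and 5% with three. With eight it exceeds 80% in the opposite direction. With one pre-treatment test, skewed values lower the 90% to about 75%, and serial correlation of 0.8 lowers it to 77%.

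**Measures that do not grow with k.** The expected proportion of tests above 0.2 is p for any k, so one and four tests give 5% and 5%. In simulation its mean difference was within 0.0005 of zero (k = 3, 4, 6). Paired t tests on individual means rejected in 4-6% of runs.

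**The case against.** The strongest reply is that one pre-treatment test is a floor. The schedule is labelled a minimum, and charts and the electronic record are reviewed. Individual profiles are to be plotted from two months before baseline, and these are established PN patients. Earlier INR and platelet results are therefore plausible, though not required; earlier fatty-acid profiles are less so. This stands. It limits the size of the shift and makes the INR and platelet comparisons less certain to be biased. It does not rescue the contrast, which then depends on each child's testing history.

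The harm is also bounded. The primary analysis is descriptive, and at the minimum schedule the error is a false alarm. If deficiency is as rare as the animal-studies section expects, the shift is about one patient in 30. Undistorted summaries are planned as well: "We will describe trends over time for all outcomes associated with fatty acid profiles"; "We will also describe the rate with which INR ratios were" above 2, per follow-up time; individual means; and repeated-measures trends. All of this stands, but none of it changes the stated 'at any time' contrast.

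A reader might infer three stronger things that the documents do not support:

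- **That the trial must show a false rise.** This holds only at, or near, the minimum schedule.
- **That 90% is the trial's error rate.** It belongs to a secondary test on maxima with a single pre-treatment value and falls to 5% at equal counts.
- **That the safety assessment as a whole is biased.** The on-treatment 'ever' outcome read alone is not affected.

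**Conclusion.** The concern holds in this limited form. The stated before/after contrast on triene/tetraene above 0.2 at any time measures testing intensity along with treatment. At the required minimum schedule it moves against Omegaven with no true change. That direction needs only one test before, two or more after, and some variation within patients.

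The size rests on assumed rates and counts. With one test against four it is 1% against 2.5-4%, or 5% against 12-19%. It vanishes at equal counts and reverses if pre-treatment tests are more numerous. The maximum and minimum comparisons share the fault wherever counts differ, less surely for INR and platelets. The secondary McNemar test is hardly affected at 1-2% per test with up to four on-treatment tests. The change should be made, because the contrast serves hypothesis 1.1 and the remedy is cheap.

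**What to change.** 1. Lead the before/after contrast for hypothesis 1.1 with each patient's proportion of tests with triene/tetraene above 0.2 in each period. Support it with individual mean values, on a log scale if skewed; the Data Analysis Plan already allows both means and transformation.
2. Use individual means likewise for INR and platelets.
3. Report 'ever', maximum and minimum for the on-treatment period only, with the number of tests and follow-up time.
4. As support, pair the last value before Omegaven with a pre-specified late on-treatment value.
5. State which on-treatment window applies to this contrast, and define the window before treatment. Report how many patients have no pre-Omegaven result and leave them out of the paired contrast.

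**Cost.** Analysis wording only; no new data. Brief or late rises weigh less in the contrast. For example, ratios of 0.05 on four tests and 0.25 on two average (0.20 + 0.50)/6 = 0.117, below the threshold, although 2/6 = 33% of tests exceed it. That is why the proportion should lead and the mean support. Such rises stay visible in the on-treatment 'ever' and maximum and in the late-value pair. With a single pre-treatment test a patient's proportion before treatment is 0 or 100%, which is coarse but not biased by the test count.
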